#### For non-US Sites

Additional research is required for all study participants, except where retention and/or collection is prohibited by local laws or regulations, ECs, or institutional requirements.

This collection for additional research is intended to expand the translational Research and Development capability at BMS, and will support as yet undefined research aims that will advance our understanding of disease and options for treatment. It may also be used to support health authority requests for analysis, and advancement of pharmacodiagnostic development to better target drugs to the right participants. This may also include genetic/genomic exploration aimed at exploring disease pathways, progression, and response to treatment etc.

## Sample Collection and Storage

All requests for access to samples or data for additional research will be vetted through a diverse committee of the study sponsor's senior leaders in Research and Development (or designee) to ensure the research supports appropriate and well-defined scientific research activities.

• Residual samples (see Table 9.8.4-1) will be retained for additional research purposes Samples kept for future research will be stored at the BMS Biorepository in an independent, BMS approved storage vendor.

The manager of these samples will ensure they are properly used throughout their usable life and will destroy the samples at the end of the scheduled storage period, no longer than fifteen (15) years after the end of the study or the maximum allowed by applicable law.

Transfers of samples by research sponsor to third parties will be subject to the recipient's agreement to establish similar storage procedures.

Samples will be stored in a coded fashion, and no researcher will have access to the key. The key is securely held by the investigator at the clinical site, so there is no direct ability for a researcher to connect a sample to a specific individual.

Further details of sample collection and processing will be provided to the site in the procedure manual.

Table 9.8.4-1: Residual Sample Retention for Additional Research Schedule

[figure not shown]
Sample Type	Timepoints for which residual samples will be retained
Serum/Plasma (including PK/IMG samples)	All
Peripheral Blood	All
	All

Protocol Amendment No.: 07

Abbreviations: IMG, immunogenicity; PK, pharmacokinetics.

# 9.8.5 Methods to Detect HPV Status of SCCHN Originating in the Oropharynx

HPV status for oropharyngeal cancer must be determined locally described below. If HPV status was previously determined using an acceptable method listed below, re-testing is not necessary.

Protocol Amendment No.: 07

# 9.9 Health Economics OR Medical Resource Utilization and Health Economics

• Number and duration of medical care encounters, including surgeries, and other selected procedures (inpatient and outpatient)

- Duration of hospitalization (total days length of stay, including duration by wards; eg, intensive care unit)
- Number and character of diagnostic and therapeutic tests and procedures
- Outpatient medical encounters and treatments (including physician or emergency room visits, tests and procedures, and medications).

### 10 STATISTICAL CONSIDERATIONS

## 10.1 Sample Size Determination

## 10.1.1 Parts 1A and 1B

Participants will be dosed in Cohorts 1B1, 1B2, and 1B3, and may be dosed in up to 4 other treatment regimens based on PK, pharmacodynamic, and/or safety analyses (Cohorts 1B4, 1B5, 1B6, Approximately participants will be initially dosed in the treatment arm(s) of interest in Part 1.

Approximately 4 participants were treated initially with BMS-986253 2400 mg in combination with 480 mg nivolumab Q4W in Part 1A. With no safety concern identified, participants will be randomly assigned in an approximately 1:1:1 allocation ratio into 3 dose combinations, BMS-986253 2400 mg, 1200 mg, and 600 mg Q4W in combination with 480 mg nivolumab Q4W. See Section 7.4 for details regarding randomization.

There will be continuous analysis . If these analyses indicate that further assessment of a treatment regimen is not warranted and/or a need for assessing additional treatment regimens is indicated, then the randomization will be stopped, and subsequent participants will be assigned sequentially to either existing treatment regimens, or treatment regimens with alternative dosing schedules. The highest dosing regimen used will be 3600 mg BMS-986253 Q2W in combination with 480 mg nivolumab. If any dosing regimen evaluates a higher dose of BMS-986253 than previously explored, an initial 4-participant safety lead-in with a 28-day DLT period will be required.

[figure not shown]

Date: 17-May-2024 176

## 10.1.2 Part 1C

The purpose of Part 1C is to generate safety data on the triplet combination of BMS-986253, nivolumab, and ipilimumab. Although the number of participants is not based on statistical power considerations,

### 10.1.3 Part 2

The purpose of Part 2 is to evaluate efficacy and gather additional safety, tolerability, PK, and pharmacodynamic information between BMS-986253 RP2D in combination with nivolumab and ipilimumab versus placebo in combination with nivolumab and ipilimumab. Participants with anti-PD-(L)1-refractory unresectable or metastatic melanoma (non-ocular) who have not been treated with prior anti-CTLA-4 therapy will be randomly assigned in a 1:1 ratio to 1 of 2 treatment arms.

# 10.2 Populations for Analyses

Population	Description	
Enrolled/Randomized	All participants who have signed informed consent and are registered into the IRT	
Treated	All participants who received at least 1 dose of study treatment	
Efficacy	All participants who take at least 1 dose of their planned full combination treatment.	
Response-evaluable	All treated participants with measurable disease at baseline and one of the following: (1) at least 1 post-baseline tumor assessment, (2) clinical progression, or (3) death	
Pharmacokinetic	All treated participants who have evaluable concentration-time data	

Population	Description
Immunogenicity	All treated participants who have baseline and at least one post baseline immunogenicity assessment
Biomarker	All treated participants with available biomarker data

Abbreviation: IRT, Interactive Response Technologies.

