Medical History	Х	All medical history relevant to the disease under study, and COVID-19 vaccines more than 30 days prior to first study treatment.  Include any toxicities or allergy related to previous treatments.
Prior Cancer Therapies	X	Including all prior cancer treatment regimens and medications administered.

Protocol Amendment No.: 07

 Table 2-2:
 Screening Procedural Outline (All Study Phases)

Procedure	Screening Visit Day -28 to Day -1	Notes
IRT Assignment	Х	After completing all screening procedures, utilize IRT to either screen fail or obtain assignment information, as applicable. Assignment can occur up to 3 days prior to first dose.
Tumor Type Assessment		
Body Imaging	X	Contrast enhanced CT/MRI of the chest, abdomen, pelvis, and all other known/suspected sites of disease. Images will be acquired within 28 days prior to the first treatment dose. Images acquired as part of care prior to signing the ICF, but within the 28-day limit, will be acceptable if there is no intervening treatment, and all required scanning acquisition parameters are met (if feasible per local regulations).  For participants with SCCHN, a CT or MRI of the neck is required.  For participants with HCC, imaging of the abdomen should include multi-phasic (at least three of the following four phases: precontrast, arterial, venous, delayed) CT or MRI of the liver.  See Section 9.4.1 for further details.
Brain Imaging	X	Part 1: At screening, MRI of the brain without and with contrast is required for participants with known or suspected brain metastases who have not had brain imaging within 28 days of anticipated first study drug administration.  Part 2: MRI of the brain (without and with contrast) is required for ALL participants during screening to rule out evidence of progression for brain metastases within the 28 days prior to treatment.  CT of the Brain (without and with contrast) can be performed if MRI is contraindicated. See Section 9.4.1 for further details. Images will be acquired within 28 days prior to the first treatment dose. Images acquired as part of care prior to signing the ICF, but within the 28-day limit, will be acceptable if there is no intervening treatment, and all required scanning acquisition parameters are met (if feasible per local regulations).
Other Bone Scan	X	As clinically indicated per local standards. See Section 9.4.1 for further details.

Protocol Amendment No.: 07

 Table 2-2:
 Screening Procedural Outline (All Study Phases)

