# 4 OBJECTIVES AND ENDPOINTS

Table 4-1: Objectives and Endpoints - Part 1

Objectives	Endpoints
Primary	
To characterize safety, tolerability, and DLTs, and to determine the RP2D of BMS-986253 administered in combination with nivolumab, or in combination with nivolumab and ipilimumab in participants with advanced solid tumors.	Incidence of AEs, SAEs, AEs meeting protocol- defined DLT criteria, and AEs leading to discontinuation, death, and laboratory abnormalities.
Secondary	

 
To evaluate the preliminary efficacy of BMS-986253 in combination with nivolumab in participants with advanced solid tumors using RECIST v1.1.
 
To characterize the PK and immunogenicity of BMS-986253 when administered in combination with nivolumab, or in combination with nivolumab and ipilimumab in participants with advanced solid tumors.
 
To assess serum IL-8 levels at baseline (ie, screening) and changes in IL-8 levels on treatment.
 
	
 
ORR and DOR per RECIST v1.1 per investigator.
 
Summary measures of PK parameters and incidence of ADA to BMS-986253.
 
Summary measures of IL-8 and change (or percent change) from baseline in IL-8 on treatment.
 

Abbreviations: ADA, anti-drug antibody; AE, adverse event; DLT, dose-limiting toxicity; DOR, duration of response; EOT, end of treatment; ORR, objective response rate; PK, pharmacokinetic(s);

Protocol Amendment No.: 07

RECIST, Response

Evaluation Criteria in Solid Tumors; RP2D, recommended Phase 2 dose; SAE, serious adverse event.

[figure not shown]
Table 4-2: Objectives and Endpoints - Part 2

	Objectives	Endpoints
Pri	imary	
•	To compare the ORR of BMS-986253 plus nivolumab plus ipilimumab with placebo plus nivolumab and ipilimumab using RECIST v1.1.	ORR based on BICR assessments per RECIST v1.1 in all randomized participants.
Sec	condary	
•	To estimate PFS of BMS-986253 plus nivolumab plus ipilimumab and placebo plus nivolumab and ipilimumab in participants with advanced melanoma using RECIST v1.1 (regardless of baseline serum IL-8 levels).	mPFS and PFS hazard ratio based on BICI assessments per RECIST v1.1.
•	To compare the safety of BMS-986253 plus nivolumab plus ipilimumab with placebo plus nivolumab plus ipilimumab in participants with advanced melanoma.	discontinuation, death, and laborator

Protocol Amendment No.: 07

Date: 17-May-2024 68

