## 5.3 End of Study Definition

The date the first participant signs a study-specific ICF will be defined as the start of the study. A participant is considered enrolled when the study-specific ICF is signed. The date the last participant completes discharge procedures or last follow up visit will be defined as the end of the study.

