### 6.4 Screen Failures

Screen failures are defined as participants who consent to participate in the clinical study but who are not subsequently randomized/entered in the study/included in the analysis population. A minimal set of screen failure information is required to ensure transparent reporting of screen failure participants, to meet the Consolidated Standards of Reporting Trials (CONSORT) publishing requirements, as applicable, and to respond to queries from regulatory authorities. Minimal information includes date of consent, demography, screen failure details, eligibility criteria, and any serious AEs.

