## 7.4 Method of Treatment Assignment and Stratification

During the pre-screening visit, the investigative site will enroll the participant in IRT for assignment of a unique 5-digit participant number designated by BMS. Enrolled participants, including those not dosed, will be assigned sequential participant numbers starting with The participant identifier number (PID) will ultimately be comprised of the site number and participant number. For example, the first participant screened (ie, enrolled) at site number 1, will have a PID of To distinguish Part 1 and Part 2 participants, the first digit of the participant number will always be a 2 for Part 2 participants Once it is determined that the participant meets the eligibility criteria following the screening visit, the investigative site will utilize the IRT to centrally assign the participant into the open dose panel (Part 1) or blinded treatment arm (Part 2). Study treatment will be dispensed at the study visits as listed in Schedule of Activities (Section 2).

#### Part 1

provides a summary of treatment assignment in Part 1. The safety evaluation lead-in (Part 1A) will start with a cohort of participants dosed at 2400 mg of BMS-986253 combined with 480 mg of nivolumab Q4W.

[figure not shown]
After the review of clinical safety assessment of the first 4 participants, the DLT, and the totality of available data, up to

assessment of the first 4 participants, the DLT, and the totality of available data, up to approximately additional participants will be enrolled in the dose-finding phase (Part 1B). Participants will be randomly assigned in an approximately 1:1:1 ratio to Cohorts 1B1, 1B2, and 1B3. Randomization will be performed using an equal randomization with each cohort capped at approximately participants, such that corresponding entries for capped cohort in the randomization list will be skipped.

In the event that the safety lead-in evaluation recommends to evaluate a lower dose of BMS-986253 (1200 mg) prior to start of the randomized dose-finding phase (Part 1B), a cohort of 4 participants will be treated in combination with 480 mg of nivolumab. If there are no safety concerns after the clinical safety assessment, then participants will be randomized in a similar fashion in approximately 1:1 ratio to Cohorts 1B2 and 1B3.

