If PK, pharmacodynamic, and/or safety analyses indicate further assessment of a dosing regimen is not warranted and/or assessment of additional dosing regimens is indicated, then randomization will be stopped, and subsequent participants will be assigned sequentially to dosing regimens available at that time. If any dosing regimen evaluates a higher dose of BMS-986253 than previously explored, an initial 4-participant safety lead-in with a 28-day DLT period will be required. Approximately participants will be dosed in the dosing regimen(s) of interest. Additional exploration of a specific dosing regimen may be warranted, in which case a maximum of approximately additional participants will be assigned to a dosing regimen of interest in Part 1B. A maximum of approximately participants will be dosed in Part 1B.

Part 1C is a safety evaluation of BMS-986253 in combination with nivolumab and ipilimumab. Part 1C will begin once the DLT period is completed for Cohort 1B6 (BMS-986253 3600 mg Q2W + nivolumab 480 mg Q4W), and will enroll simultaneously with Part 1B. In Part 1C, participants

Protocol Amendment No.: 07 Date: 17-May-2024

Protocol Amendment No.: 07

#### Part 2

Part 2 will begin after determination of the RP2D from Part 1 and generating safety data on the triplet combination of BMS-986253 plus nivolumab plus ipilimumab in Part 1C. Part 2 is a double-blind randomized evaluation of BMS-986253 plus nivolumab plus ipilimumab versus placebo plus nivolumab plus ipilimumab and will be conducted to evaluate the efficacy of BMS-986253 in participants who are refractory to anti-PD-(L)1 therapy.

IRT will be used to track the enrollment number.

Once assigned a subject ID in IRT, participants that have met all eligibility criteria will be randomized through IRT (up to 3 days prior to C1D1). The following information is required prior to participant randomization:

- Participant subject ID
- Date of birth
- Gender
- Screening serum IL-8 level

• Screening LDH

Participants will be randomized in a 1:1 ratio to treatment and control arms. Three stratification factors will be used during randomization: screening

and screening LDH (≤ ULN or > ULN). Screening serum IL-8 data will be transferred directly from the analyzing laboratory to IRT. BRAF status and screening LDH must be entered in eCRF by the site.

Approximately participants will be randomized in Part 2.

The exact procedures for using the IRT will be detailed in the IRT manual.

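### Section 10.2 defines no set of participants randomized to 2A or 2B, and Section 10.3.1 puts the main efficacy analyses on a dosed set instead of all randomized participants

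*Combined protocol and SAP*

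**What the plan says.** Section 4, Table 4-2 gives the Part 2 primary endpoint as "ORR based on BICR assessments per RECIST v1.1 in all randomized participants". Section 5.4.3 likewise refers the Part 2 primary endpoint to all randomized participants, whatever their baseline serum IL-8.

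Section 10.2 has a single row labelled Enrolled/Randomized, defined as "All participants who have signed informed consent and are registered into the IRT". The next two rows are Treated (any dose of study treatment) and Efficacy (one or more doses of the complete planned combination). No row is defined by assignment to an arm.

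Section 10.3.1 says that the main efficacy analyses at the final analysis use the Efficacy population. It does not limit this to Part 1. Table 10.3.1-2 defines the Part 2 ORR only over a population of interest, without naming it.

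On the order of events, Section 7.4 (Part 2) says "Once assigned a subject ID in IRT, participants that have met all eligibility criteria will be randomized through IRT", and Table 2-2 in Section 2 says "After completing all screening procedures, utilize IRT to either screen fail or obtain assignment information, as applicable". Section 5.3 says "A participant is considered enrolled when the study-specific ICF is signed".

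**The concern.** The primary analysis of a randomized comparison needs one stated set of participants. The readable text points to three:

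- Table 4-2 names all randomized participants.
- The row in Section 10.2 that bears that name is wider, because consent and registration are enough to enter it.
- The set that Section 10.3.1 assigns is narrower, because entry depends on treatment received after randomization.

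The narrower set matters more. If the primary ORR is run on participants who received the full combination, membership is decided after allocation, and the groups compared are no longer exactly those that randomization formed. An unsettled denominator also leaves a choice open near database lock, where it could later be questioned as data-driven.

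**Working it through.** There is no stated figure to reproduce. In the readable text the Part 2 sample size and assumed rates are blank, so the check sets the definitions side by side.

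**Step 1: does the Enrolled/Randomized row mean randomized?** Under Section 7.4 a Part 2 participant first holds an IRT subject ID, and only those who meet all criteria are then randomized. Under Table 2-2 the IRT is also where a screen failure is recorded. A Part 2 participant who signs consent, is registered and then fails screening therefore satisfies "All participants who have signed informed consent and are registered into the IRT" without ever having an arm. Section 7.4 also uses screened and enrolled as synonyms ("the first participant screened (ie, enrolled) at site number 1"). This agrees with Section 5.3 but does not make such a person randomized. The row describes an enrolled set.

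**Step 2: does another row supply the randomized set?** Treated, Efficacy, Response-evaluable, Pharmacokinetic, Immunogenicity and Biomarker all require treatment. None equals assignment to 2A or 2B.

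**Step 3: does the Efficacy population equal all randomized participants?** Randomization may take place up to 3 days before the first dose (Section 7.4), so a participant can be randomized and never dosed. A participant can also start treatment without receiving every agent of the combination. Both are randomized, and both fall outside the Efficacy population.

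**Step 4: how much could this change the result?** In one arm, let N_R be the number randomized, N_E the number in the Efficacy population, and x the number of responders among the N_E. If nobody outside the Efficacy population has a confirmed response by central review:

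- ORR on the Efficacy population = x / N_E
- ORR on all randomized = x / N_R = (x / N_E) × (N_E / N_R)

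The ratio N_E / N_R is at most 1, so the rate on all randomized is the same or lower. If the ratio is equal in the two arms, both rates and their difference shrink by that factor. If it differs between arms, the difference can move either way. The documents give neither N_E nor N_R, so no value follows.

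**Step 5: is there a rule for participants without scans?** Sections 5.1.6 and 9.4 describe central review of scans for treated participants, and Table 10.3.1-2 counts best overall response from the first dose. The readable text does not say expressly how a randomized but undosed participant counts.

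**The case against.** The case on the other side has four parts.

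First, the meaning of randomized is clear elsewhere. Section 6.4 describes screen failures as "participants who consent to participate in the clinical study but who are not subsequently randomized/entered in the study/included in the analysis population", and Section 7.4 reserves randomization for those who meet all criteria. This stands as evidence of intent: screen failures are very probably not meant to be counted. It does not correct the table, and it conflicts with it.

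Second, Section 10.3.1 controls the analysis, and the Efficacy population contains no screen failures. That is true, but it replaces a set that is too wide with one that is too narrow, and the contradiction with Table 4-2 remains.

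Third, Section 10.3 leaves the selection of participants to a statistical analysis plan to be finalized before database lock. The combined document contains no separate plan text, so a later definition may settle the matter. That limits the point without answering it.

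Fourth, counting participants without an assessment as non-responders already follows from ORR as a proportion of the population. On a plain reading it does. An explicit sentence is still useful, because central review and best overall response are both tied to treatment.

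A reader might also infer that screen failures would dilute the primary ORR, and might multiply a response rate by one minus an assumed screen-failure share. The documents do not support this. Table 10.3.1-2 compares two treatment groups, and a screen failure belongs to neither, so no planned analysis would yield such a figure.

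**Conclusion.** The point holds as a defect of definition and a contradiction about the primary analysis set. Section 10.2 has no population equal to the participants randomized to 2A or 2B. Section 10.3.1 directs the main efficacy analyses to a set that excludes some participants after randomization, against Table 4-2. It should be corrected before database lock.

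Its size is unknown. It depends on how many randomized participants never received a dose of the full combination, which the readable text does not state. If there are none, the Efficacy population and the randomized set coincide and only the wording is at fault. Double-blinding in Part 2 makes exclusions before the first dose unlikely to depend on the arm, so no bias is demonstrated.

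A reader might go further and conclude that the randomized comparison has no valid analysis set at all. That is too strong, because the participants assigned to each arm can be identified from the IRT. What is missing is a definition that says so and an analysis section that uses it.

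The conclusion assumes that no redacted text in Sections 10.1.3 or 10.3.1, and no separate analysis plan, names the set by assigned arm.

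**What to change.** In Section 10.2, split the row in two:

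- **Enrolled:** consent signed and registered in the IRT.
- **Randomized (Part 2):** assigned to 2A or 2B by the IRT, analysed in the assigned arm whether or not dosed.

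In Section 10.3.1, state that the Part 2 primary ORR comparison uses the Randomized set. State also that any participant without a confirmed complete or partial response by central review counts as a non-responder, including those undosed or without a post-baseline scan. Keep the Efficacy population for the Part 2 ORR as a sensitivity analysis. Part 1 need not change. Carry the same wording into the analysis plan before database lock.

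The cost is a few lines of text, with no extra data or visits. The reported ORR may be slightly lower in each arm than on the Efficacy population.
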